The primary objective of this study is to evaluate the efficacy of nebulized heparin administration in COVID-19. Our primary outcome will be defined as the mean PaO₂/FiO₂ ratio in the first 10 days of ICU stay. This is the gold standard for hypoxia monitoring in ARDS. Our secondary safety outcome will include clinically significant bleeding, defined as transfusion of red blood cells, required intervention for new-onset bleeding, or death attributed to bleeding during the study period. Additional outcomes will include incidence of VTE, time on mechanical ventilation, ICU duration, and overall mortality.

Study Design: Describe the study design (e.g., single/double blind, parallel, crossover, etc.). Indicate whether or not the subjects will receive placebo medication at some point in the research procedures. Also, indicate whether or not the subjects will be randomized in this study. You may reference sponsor's protocol pages and attach as an appendix in the E-IRB "Additional Information" section, however, a summary paragraph must be provided in the text box below. (Including the study design table from a sponsor's protocol is helpful to IRB members.)

Community-Based Participatory Research: If you are conducting community-based participatory research (CBPR), describe strategies for involvement of community members in the design and implementation of the study, and dissemination of results from the study.

Research Repositories: If the purpose of this submission is to establish a Research Repository (bank, registry) indicate whether the material you plan to collect would or would not be available from a commercial supplier, clinical lab, or established IRB approved research repository. Provide scientific justification for establishment of an additional repository collecting duplicate material. Describe the repository design and operating procedures. For relevant information to include, see the UK Research Biospecimen Bank Guidance [PDF] or the UK Research Registry Guidance [PDF]

We propose a randomized, controlled pilot study of patients admitted with confirmed COVID-19 receiving mechanical ventilation for ARDS (paO₂/FiO₂ ratio =300) within 48 hours. Enrollment will occur by the ICU research team who perform daily review for study enrollment. Patients will be randomized to nebulized heparin (25,000 units in 3 mL sodium chloride [NaCl] every 6 hours) versus

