Provide the following information:

- A description of the subject selection criteria and rationale for selection in terms of the scientific objectives and proposed study design;
- A compelling rationale for proposed exclusion of any sex/gender or racial/ethnic group;
- The proposed dates of enrollment (beginning and end);
- The proposed sample composition of subjects.

You may reference grant application/sponsor's relevant protocol pages and attach as an appendix using the below attachment button, however, a summary paragraph must be provided in the text box below.

Patients admitted with confirmed COVID-19 receiving mechanical ventilation for ARDS ($\text{paO}_2/\text{FiO}_2$ ratio =300) will be included.

Patients will be excluded for the following:

- Allergy to heparin
- Any history of heparin-induced thrombocytopenia
- High risk of bleeding (platelet count < 50,000/ μ L or international normalized ratio > 1.5)
- Patients with known bleeding disorders (i.e. hemophilia or von Willebrand Disease)
- Active bleeding
- Pulmonary bleeding during this hospital admission (Pulmonary bleeding is frank bleeding in the lungs, trachea or bronchi with repeated hemoptysis, or requiring repeated suctioning, and temporally associated with acute deterioration in respiratory status)
- Neurosurgical procedures during this hospital admission or such procedures are planned
- Epidural catheter in place
- Any history of intracranial, spinal or epidural hemorrhage
- Tracheostomy in place
- Cervical spinal cord injury associated with reduced long-term ability to breathe independently
- Spinal or peripheral nerve disease with a likely prolonged reduction in the ability to breathe independently
- Receiving extra-corporeal membrane oxygenation or continuous renal replacement therapy
- Usually treated with hemodialysis or peritoneal dialysis for end-stage renal failure
- Death is deemed imminent or inevitable or there is an underlying disease with a life expectancy of fewer than 90 days
- Pregnant or might be pregnant.
- Objection from the treating clinician
- Consent refused by the patient or substitute decision maker.
- History of thrombosis (VTE or cardiovascular event)

Attachments

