Patients will be screened for eligibility by a member of the research team. If a patient meets eligibility, then a team member will approach the LAR for informed consent. After enrollment, the patient will be randomized via an online randomization generator to either nebulized heparin (25,000 units in 3 mL sodium chloride [NaCl] every 6 hours) or placebo (5 mL nebulized NaCl every 6 hours) for 10 days or until successful ventilator wean. The nurse will be approached for a 10 mL blood draw to be performed at baseline, 72 hours, and day 10 to assess protein S, thrombin, and histone in the [name] laboratory (BBSRB B306-15 and B306-16). The study team will collect the blood samples. Up to 10 mL of blood will be drawn each time for a maximum of 30 mL total, collected in citrate-containing tubes. Deidentified data will be collected via RedCap from the standard of care charting. Upon study completion, deidentified data will be sent to the statistician for analysis.

Attachments

Data Collection: List the data or attach a list of the data to be collected about or from each subject (e.g. interview script, survey tool, data collection form for existing data).

If the research includes survey or interview procedures, the questionnaire, interview questions or assessment scales should be included in the application (use attachment button below).

The data collection instrument(s) can be submitted with your application in draft form with the understanding that the final copy will be submitted to the IRB for approval prior to use (submit final version to the IRB for review as a modification request if initial IRB approval

was issued while the data collection instrument was in draft form).

Note: The IRB approval process does not include a statistical review. Investigators are strongly encouraged to develop data management and analysis plans in consult with a statistician.

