Computers: Computers are available to the study team in [name] laboratory and office. These computers are part of the UK health center network and require UK login credentials. Once logged in, study team members will have access to the shared folder where study-related documents are stored. Anyone who is not a member of the study team will not have access to this folder. In addition, non-identifiable results will be stored in a LabArchives folder, to which study team members will have access.

Potential Risks: Describe any potential risks or likely adverse effects of the drugs, biologics, devices or procedures subjects may encounter while in the study. Please describe any physical, psychological, social, legal or other risks and assess their likelihood and seriousness.

Risks associated with drawing blood from the intravenous line are minimal, but may include discomfort, bruising, soreness, infection, excess bleeding, clotting, light headedness, or fainting. Risks of nebulized heparin, although rare, include bleeding and an increase in partial prothrombin time.

[Back to Top](#)

Safety Precautions: Describe the procedures for protecting against or minimizing any potential risks, *including risks of breach of confidentiality or invasion of privacy*. Where appropriate, discuss provisions for ensuring necessary medical or professional intervention in the event of adverse events, or unanticipated problems involving subjects. Also, where appropriate, describe the provisions for monitoring the data collected to ensure the safety of subjects. If vulnerable populations other than adults with impaired consent capacity are to be recruited, describe additional safeguards for protecting the subjects' rights and welfare.

Researchers will take steps to keep the information confidential. Researchers will not list identifiable information on samples stored in the laboratory, but use a key linked back to a master list maintained on a password-protected computer. The patients will be in the

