intensive care unit and subject to the intensive monitoring required from the baseline care of such a population. Once the database has been completed from information collected, identifiable information will be removed and replaced with a subject ID number. The PI will maintain a logbook of the ID number with patient identifiers in a locked cabinet in a locked office. If clinically significant bleeding occurs during drug treatment, defined as transfusion of red blood cells thought to be secondary to investigational drug or required intervention for new-onset bleeding secondary to investigational drug, the drug will be automatically stopped.

Benefit vs. Risk: Describe potential benefits to the subject(s); include potential benefits to society and/or general knowledge to be gained. Describe why the risks to subjects are reasonable in relation to the anticipated benefit(s) to subjects and in relation to the importance of the knowledge that may reasonably be expected to result. If you are using vulnerable subjects (e.g., impaired consent capacity, pregnant women, etc...), justify their inclusion by describing the potential benefits of the research in comparison to the subjects' vulnerability and the risks to them. For information about inclusion of certain vulnerable populations, see the IRB/ORI Standard Operating Procedure for Protection of Vulnerable Subjects [C3.0100] [\[PDF\]](#).

We do not know if subjects in this group will benefit directly, but hypothesized benefits of the use of nebulized heparin include decreased length of stay and decreased lung injury scores. Risks are outlined in the informed consent document and notably include the risk of bleeding. Given the mortality rate in patients with ARDS secondary to COVID-19, there may be patients that benefit from this drug despite the minimal risks. We have attempted to use the literature to guide our protocol to reflect those patients most likely to benefit.

Available Alternative Treatment(s): Describe alternative treatments and procedures that might be advantageous to the subjects, should they choose not to participate in the study. This should include a discussion of the current standard of care treatment(s).

There are no alternative treatments. Patients enrolled will continue to receive standard of care therapies per the discretion of the primary team. Thromboprophylaxis is permitted per standard of care. Patients who require systemic anticoagulation will be excluded from this study.

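### The bleeding stop rule does not require study drug to be held during an on-treatment pulmonary bleed unless transfusion or intervention is blamed on the drug

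*Protocol*

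**What the plan says.** **Entry.** The exclusion list in Study Population includes "Pulmonary bleeding during this hospital admission". The definition follows: "Pulmonary bleeding is frank bleeding in the lungs, trachea or bronchi with repeated hemoptysis, or requiring repeated suctioning", together with an acute worsening of respiratory status close in time. It sets no condition on cause, on transfusion or intervention, or on whether the bleed has ended. Active bleeding at any site is a separate exclusion.

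**Dosing.** Study Design and Research Procedures give heparin as "25,000 units in 3 mL sodium chloride [NaCl] every 6 hours", continued "for 10 days or until successful ventilator wean". Neither section attaches a bleeding condition.

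**Stopping.** Safety Precautions contains the only bleeding rule in the protocol that acts on dosing. Its triggers are "transfusion of red blood cells thought to be secondary to investigational drug or required intervention for new-onset bleeding secondary to investigational drug", and the consequence is stated at its end: "required intervention for new-onset bleeding secondary to investigational drug, the drug will be automatically stopped".

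**Recognized risk.** Potential Risks states: "Risks of nebulized heparin, although rare, include bleeding and an increase in partial prothrombin time". The Background says nebulization gives a higher dose in the respiratory tract while lowering the risk of systemic bleeding.

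**General oversight.** Data and Safety Monitoring has the investigators review all adverse events routinely. It names no bleeding criterion and no consequence for dosing.

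**The concern.** Heparin is delivered to the airway, so a frank airway bleed with acute deterioration is the event for which a mandatory pause matters most. The protocol already takes this view at entry. Once treatment has begun, the mandatory stop depends on someone deciding that study drug caused the transfusion or the intervention.

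That decision is hard to make for one patient. COVID-19 lung injury is a ready alternative explanation, and thromboprophylaxis, which the protocol permits, is another. The comparison is with placebo: an assessor who does not know the arm is partly guessing, and one who does know it may let the arm sway the judgement.

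What is at stake is the safety of individual patients during an airway bleed. No bias in the primary oxygenation outcome is claimed.

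**Working it through.** The protocol gives no figure to reproduce, so the check sets the two rules side by side.

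**Inputs.** Let B be a pulmonary bleed meeting the Study Population definition, T a red-cell transfusion, I a required intervention for new-onset bleeding, and A a judgement that the T or I is secondary to study drug.

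- Entry rule (Study Population): withhold if B. A, T and I play no part.
- Stop rule (Safety Precautions): stop if (T and A) or (I and A), that is, A and (T or I). B plays no part.

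**Applying both rules to the same bleed B:**

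| Features of the bleed | Before randomization | On treatment |
|---|---|---|
| T or I, attributed to study drug | Excluded | Stop required |
| T or I, attributed to COVID-19 or another cause | Excluded | No stop required |
| Neither T nor I, any attribution | Excluded | No stop required |

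In the second and third rows the only stated dosing instruction is to continue to day 10 or to successful wean. At one dose every 6 hours, that is 24 / 6 = 4 scheduled doses a day.

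**How much depends on the meaning of intervention?** The protocol does not define a required intervention. If repeated suctioning counts as one, every bleed that qualifies through the suctioning limb has I, and the third row shrinks. The second row is unaffected, because A is still needed. The gap therefore survives the reading most favourable to the protocol, and the attribution condition is what sustains it.

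**How many patients?** The protocol gives no rate of pulmonary bleeding. The only safety rates it quotes are for adverse events in an earlier randomized ARDS trial: 5% of 128 heparin patients and 2% of 124 placebo patients. As an illustration only, taking a rate r to apply to the 23 planned heparin patients:

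- r = 2%: 23 × 0.02 = 0.46
- r = 5%: 23 × 0.05 = 1.15, about 1.2

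The Background does not say what those events were, and the population may differ, so this is neither an estimate nor a bound for pulmonary bleeding in this trial. Bleeds in the second and third rows would be only part of all pulmonary bleeds.

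**The case against.** **Entry criteria and stop rules do different jobs.** A low platelet count, a raised INR, an epidural catheter, a tracheostomy and continuous renal replacement therapy also bar entry, and none is a stop trigger. A reader might infer that the protocol contradicts itself by excluding a bleed the day before randomization and dosing through it the day after. The documents do not support that: exclusion at entry alone is the protocol's general pattern. The proposed hold also keeps some asymmetry, since a resolved bleed would still bar entry but would allow dosing to resume. This objection stands against any charge of contradiction. It does not answer the narrower point about a bleed in progress at the site of drug delivery.

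**The gap is narrow and partly covered.** The definition requires frank bleeding and acute deterioration, suctioning may count as intervention, and the transfusion trigger asks only that a link to the drug be thought present. Patients are under intensive care, adverse events are reviewed, and nothing forbids an earlier stop. The attribution condition applies to bleeding at every site, not only the lung. All of this stands and limits the size of the point. Discretion and review are still not the same as a required hold.

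**Other documents may cover it.** The study drug form and the consent forms are attached but not shown, and could carry further stopping instructions. This cannot be excluded.

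**Two further readings should not be drawn.** One is that these bleeds escape safety reporting. The secondary safety outcome in Objectives is "clinically significant bleeding, defined as transfusion of red blood cells, required intervention for new-onset bleeding, or death attributed to bleeding", so a transfusion or intervention counts there whatever its cause, and tabulation by site can be left to the SAP or the case report form. The other is that the remaining schedule, up to 40 doses (4 × 10) over the full course, measures harm. It is a ceiling that assumes no wean and no clinician stop, and it says nothing about risk.

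**Conclusion.** The point holds as a weakness in a stated safety rule. The automatic stop covers only transfusion or required intervention judged secondary to study drug. It therefore does not require a hold during a pulmonary bleed, as the protocol defines one, that is attributed to COVID-19 or needs neither measure. The protocol's own view of that bleed at entry, and its statements about local dose and bleeding risk, are good reason to want a hold.

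The size is modest. The number of affected patients is unknown and probably small, and no event rate, excess risk or direction of bias is claimed. The conclusion assumes that no attachment outside the protocol text adds a stopping instruction. It does not assume that clinicians would in practice continue dosing, only that the rule does not require them to pause.

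**What to change.** Add one sentence to Safety Precautions: study drug, in either arm, is held for pulmonary bleeding as defined in the exclusion criteria, regardless of attribution to study drug and of whether transfusion or intervention is needed, and may resume if the bleed resolves. The existing automatic stop can stay as it is for drug-attributed events.

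Applying the hold in both arms avoids the need to know the allocation or to judge cause at the bedside. Using the existing definition means no new clinical term has to be agreed, and a hold rather than a permanent stop limits the loss of treatment exposure.

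The cost is a short protocol amendment and a few more treatment holds, some for bleeding caused by the underlying disease. The sample size and the outcome definitions do not change.

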Severe acute respiratory syndrome coronavirus 2 (SARS-CoV-2) is a novel coronavirus, emerging first in December 2019. Since then, over eight million patients have tested positive for coronavirus disease 2019 (COVID-19), with a hospitalization count exceeding 63,000 patients. (1) Over 40% of hospitalized patients with COVID-19 develop acute respiratory distress syndrome (ARDS), with mortality exceeding 60%. (2) The optimal therapeutic approach to COVID-19 ARDS remains unknown, with multiple failed trials of agents targeting SARS-CoV-2 and the resulting inflammatory response. (3-6) To date, the focus of COVID-19 supportive care research has focused on the immune response incited by this novel coronavirus; however, recent data show that the cytokine response elicited within COVID-19 is minimal relative to other ARDS populations. (7) Rather, COVID-19 ARDS appears to have a higher incidence of coagulopathy compared to historic ARDS populations. (7) Namely, COVID-19 ARDS is associated with altered plasma coagulation markers, such as increased D-dimer, increased prothrombin time, and a lower platelet count compared to alternative ARDS causes. (8-12) Pulmonary microvascular clot formation is a known feature of COVID-19 ARDS; however, such clots are commonly not identified until such clots propagate to larger, clinically detrimental venous thromboembolic events (VTE). (8-12) Microvascular thrombosis worsens pulmonary function through several mechanisms and correlates with illness severity, respiratory failure, and mortality in ARDS. (13)

COVID-19 coagulopathy has a significant impact on patient outcomes. (14) The incidence of VTE has been reported to exceed 30% in some studies. (15) Several guidelines have made recommendations regarding therapeutic systemic anticoagulation to prevent or treat VTE in COVID-19, with the majority recommending therapeutic anticoagulation only once a thromboembolic event is found or highly suspected. (16) More aggressive strategies of systemic anticoagulation for VTE prevention pose a high risk of bleeding and thus are not currently recommended. (16) While the thrombotic mechanisms in COVID-19 patients are not clear, they may involve both increased coagulation and decreased fibrinolysis. Standard anticoagulation, such as heparin, inhibits activation of coagulation, promotes anticoagulant tissue factor pathway inhibitor expression, reduces procoagulant tissue factor expression, and increases endothelial expression of heparin sulfate.

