Nebulized heparin has a potential benefit in contrast to systemic heparin, given its direct effects on the pulmonary vasculature. Because of its route of administration, higher doses are seen locally, increasing efficacy within the respiratory tract and reducing the risk of system bleeding. (13) Systemic absorption is minimal, allowing for much higher doses of heparin to be administered via inhalation compared to standard systemic doses. (17) Further, nebulized heparin has the potential to inhibit pulmonary viral replication. In previous trials of nebulized heparin for the treatment of non-COVID-19 ARDS, nebulized heparin was shown to decrease alveolar dead space fraction and tidal volumes, while also increasing days free of mechanical ventilation. (18-19) Early nebulized heparin has the potential to decrease clot formation directly at the site of onset, preventing VTE events and later the need for systemic anticoagulation while improving overall oxygenation. In a recent randomized controlled study of 256 patients with ARDS, nebulized heparin was not associated with an increase in adverse events (5% of 128 patients in the heparin group vs 2% of 124 patients in the placebo group; OR 2.33 [0.59 to 9.24]; p=0.23). (20)

Preliminary data suggest that coagulopathy is highly prevalent and potentially perpetuates COVID-19 ARDS and VTE. In our preliminary work at the University of Kentucky, we evaluated coagulation profiles in patients with COVID-19 (in-patients and outpatients) compared to control. Patients with COVID-19 had decreased plasma anticoagulant protein S. Additionally, patients with COVID-19 had more procoagulant plasma when compared to controls, and systemic anticoagulation did not appear to influence these factors. Currently, systemic anticoagulation is provided only once a known thromboembolic event occurs. We hope to prevent this resistant prothrombotic phase with the use of early inhaled heparin in contrast to systemic administration after known VTE. The objective of the current study is to investigate the utilization of nebulized heparin to circumvent this pathologic change and prevent harmful effects possible with systemic anticoagulation.

1. Coronavirus-19. CDC. Accessed October 27, 2020 from: https://gis.cdc.gov/grasp/covidnet/COVID19_5.html.

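### The exclusion of patients who require systemic anticoagulation has no time point, so read literally it could end follow-up of randomised patients because they developed VTE

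*Protocol*

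**What the plan says.** The rule stands in the Protocol, Research Description, under Available Alternative Treatment(s): "Patients who require systemic anticoagulation will be excluded from this study". Two sentences come just before it. The first concerns patients already in the trial: "Patients enrolled will continue to receive standard of care therapies per the discretion of the primary team". The second allows a concomitant treatment: "Thromboprophylaxis is permitted per standard of care". None of the three gives a time point for the exclusion.

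Eligibility is stated twice, in Study Design and as a list in Study Population that opens "Patients will be excluded for the following". Neither names systemic anticoagulation. The nearest criterion in both is a history of thrombosis.

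Under Objectives, the primary outcome is the mean PaO2/FiO2 (P/F) ratio over the first 10 ICU days, and "Additional outcomes will include incidence of VTE, time on mechanical ventilation, ICU duration, and overall mortality". Data Collection also lists VTE and pulmonary embolism. Background links VTE to the excluded treatment: "Currently, systemic anticoagulation is provided only once a known thromboembolic event occurs". It also hopes that early nebulised heparin will prevent VTE and so the later need for systemic anticoagulation. Study Design has mortality, length of stay and ventilation duration recorded through the whole hospitalisation.

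**The concern.** By the protocol's own account, a patient who develops VTE during the trial is a patient who will be given systemic anticoagulation. If the rule is applied at that moment, a randomised patient leaves because an outcome occurred, and it is an outcome that study treatment is hoped to change. That is selection after randomisation on something related to both outcome and treatment.

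The clearest loss would be what comes after the event: the remaining P/F values within the 10 days, ventilation duration and survival. Background says that microvascular thrombosis goes with greater illness severity, respiratory failure and death, so the patients removed would plausibly be sicker than average. If heparin does prevent VTE, more of them would leave the placebo arm, which would tend to pull these comparisons towards no difference. Data that were never collected cannot be recovered by any later analysis plan.

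**Working it through.** **Step 1: the passages side by side.**

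- *For a rule that operates during the trial.* It has no time limit and sits with two sentences on care during the study. It is absent from both eligibility statements. An entry-only rule would also have limited work to do: Background ties systemic anticoagulation to a known thromboembolic event, and a history of thrombosis is already an exclusion. What remains is other indications, or a new event not counted as history.
- *For an entry criterion in the wrong box.* Study Design, Study Population and the pre-screening text in the consent-waiver section all use *exclude* for eligibility. For an event during treatment, Safety Precautions uses other language: after bleeding attributed to study drug, the drug is stopped.
- *What no passage says.* Nothing states that a randomised patient who starts systemic anticoagulation is withdrawn, has data deleted or leaves the analysis. Nothing states that such a patient is kept.
- *Conflict if applied after randomisation.* Study Design collects outcomes through the whole hospitalisation and makes no exception for these patients.

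**Step 2: the plan's own sample size.** Inputs from Study Design: baseline P/F 118 mmHg, 15% improvement, alpha 0.05, power 80%, 23 per group, 46 in total. No SD is stated, so 46 cannot be reproduced from the stated inputs. It can be solved for the SD it implies:

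- difference = 0.15 × 118 = 17.7 mmHg
- SD = 17.7 / [(1.960 + 0.842) × √(2/23)] = 17.7 / (2.802 × 0.2949) ≈ 21.4 mmHg (two-sided, normal approximation)

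The two-sided t-test gives about 21.0. A one-sided normal calculation gives 24.1, since the protocol does not state sidedness. The wording problem does not depend on this figure, which serves only to scale the illustration.

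**Step 3: illustrative size.** Background supplies one VTE figure: "The incidence of VTE has been reported to exceed 30% in some studies". It is a literature remark, not a planning rate for this trial. Suppose every patient with VTE is removed and contributes nothing to the primary comparison:

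power ≈ Φ{17.7 / [21.4 × √(1/n₁ + 1/n₂)] − 1.960}

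| Share removed (placebo / heparin) | Removed of 46 | Left per arm (placebo / heparin) | Power |
|---|---|---|---|
| none | 0 | 23 / 23 | 80% (by construction) |
| 10% / 10% | 4.6 | 20.7 / 20.7 | 76% |
| 20% / 20% | 9.2 | 18.4 / 18.4 | 71% |
| 30% / 30% | 0.30 × 46 = 13.8 | 16.1 / 16.1 | 65% |
| 30% / 15% | 6.9 + 3.45 = 10.35 | 16.1 / 19.55 | 69% |

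The 10%, 20% and 15% rates are assumptions with no source in the protocol. The table shows lost precision only. It does not measure the bias from removing patients according to an outcome that treatment may affect, and the protocol gives no figures from which that bias could be calculated.

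**The case against.** The best case on the other side is that this is an eligibility criterion written in the wrong place. Elsewhere the protocol uses *exclude* for screening. The sentence says patients, not enrolled patients, although the author used the narrower term two sentences earlier. The form field asks about alternatives for people who choose not to take part, so it is not a follow-up or analysis section. The entry reading also fits the collection of VTE as an outcome and follow-up through the hospital stay. All of this stands: the entry reading is fair and may be the intended one.

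Two stronger readings are tempting. A reader might infer that the rule *would* remove randomised patients. The protocol does not say so, and it does not say whether exclusion means stopping study drug, ending follow-up or leaving the analysis. A reader might also infer that the VTE comparison would vanish from the data. That needs the further assumption that recorded events are deleted. Anticoagulation follows a known event, so the VTE would have been diagnosed first and could still be counted.

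It can also be said that the analysis set is commonly left to a statistical analysis plan, which is not at hand. That is fair for the analysis, but not for ending data collection at the bedside, which the protocol governs. Finally, the 30% is a background figure from some studies, whereas this trial excludes prior thrombosis and permits thromboprophylaxis. The figures above are therefore illustrations, not forecasts.

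**Conclusion.** The concern holds as an ambiguity with a harmful literal reading, not as a demonstrated selection on outcome. The rule has no time point, is missing from both eligibility statements and follows text on care during the study. Two staff members could reasonably apply it differently. If it were applied after randomisation, it could end follow-up for reasons related to outcome and treatment. Later P/F, ventilation and mortality data would be lost and VTE data possibly so, in conflict with the follow-up set out in Study Design.

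At the background rate of about 30%, the loss would be about 14 of 46 patients and power about 65% instead of 80%. This assumes that the rate applies here, that every patient with VTE is removed with no primary data kept, and that the two-sided SD is about 21 mmHg. The loss of power would be smaller if P/F values from before the event were used, or if some events fell after day 10. Outcome-related loss is the more serious harm, and in a trial of 46 even a few such removals matter.

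**What to change.** Reconcile Study Design, Study Population and Available Alternative Treatment(s):

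1. State whether the anticoagulation rule applies only at entry. If it does, place it in the eligibility list and in the design summary, with the time point given as randomisation.
2. Add a sentence such as: *A randomised patient who later starts systemic anticoagulation remains in follow-up for all outcomes and is analysed in the assigned arm; the start date and the reason are recorded.*

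How the anticoagulation criterion is defined, and whether study drug continues in such a patient, are clinical matters for the sponsor and clinicians to settle. The second sentence concerns follow-up and analysis only.

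The cost is about two sentences of amendment. No additional patients or procedures are needed, because outcomes and medications already come from routine charting. The small downside is that some retained patients will have mixed anticoagulant exposure, which the recorded start date and reason allow the analysis to describe.
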